---

## PROTOCOL SYNOPSIS

### **A Phase III, Randomised, Double-blind, Placebo-controlled, Multi-centre, International Study of MEDI4736 as Sequential Therapy in Patients with Locally Advanced, Unresectable Non-Small Cell Lung Cancer (Stage III) Who Have Not Progressed Following Definitive, Platinum-based, Concurrent Chemoradiation Therapy (PACIFIC)**

#### **Study centre(s) and number of patients planned**

Approximately 1000 patients with locally advanced, unresectable non-small cell lung cancer (NSCLC; Stage III) will be recruited and 702 patients randomised at 260 to 330 sites in Australia, Asia, Europe, North and South America and South Africa. These patients will be in complete response (CR), partial response (PR), or have stable disease (SD) following definitive, platinum-based, concurrent chemoradiation therapy.

Study period	Phase of development	
Estimated date of first patient enrolled	Q2 2014	3
Estimated date of last patient completed	Q2 2021	3

#### **Objectives**

Primary Objective:	Outcome Measure:
To assess the efficacy of MEDI4736 treatment compared with placebo in terms of OS and PFS	OS PFS using BICR assessments according to RECIST 1.1 a

a The co-primary analysis of PFS will be based on programmatically derived PFS BICR assessment according to RECIST 1.1. See the statistical methods section for further details.

BICR Blinded Independent Central Review; OS Overall survival; PFS Progression free survival; RECIST Response Evaluation Criteria In Solid Tumours.

Secondary Objective:	Outcome Measure:
To further assess the efficacy of MEDI4736 compared with placebo in terms of: OS24, ORR, DoR, APF12, APF18, PFS2, and TTDM	OS24 ORR using BICR assessments according to RECIST 1.1a DoR using BICR assessments according to RECIST 1.1a APF12 and APF18 using BICR assessments according to RECIST 1.1 PFS2 as defined by local standard clinical practice TTDM using BICR assessments according to RECIST 1.1a
To assess the safety and tolerability profile of MEDI4736 compared with placebo	AEs, physical examinations, vital signs including blood pressure, pulse, electrocardiograms, and laboratory findings including clinical chemistry, haematology and urinalysis
To assess the PK of MEDI4736	Concentration of MEDI4736 in blood and non-compartmental PK parameters (such as peak concentration and trough, as data allow) (sparse sampling)
To investigate the immunogenicity of MEDI4736	ADA (confirmatory results: positive or negative; titres [ADA neutralising antibodies will also be assessed])
To assess symptoms and health-related quality of life in patients treated with MEDI4736 compared with placebo using EORTC QLQ-C30 v3 and LC13	EORTC QLQ-C30: Time to symptom deterioration (fatigue, pain, nausea/vomiting, dyspnoea, loss of appetite, insomnia, constipation, and diarrhoea). Time to QoL/function deterioration (physical function; role function; emotional function; cognitive function; social function and global health status/QoL) LC13: Time to symptom deterioration (dyspnoea, cough, haemoptysis, chest pain, arm/shoulder pain, other pain) Changes in World Health Organization Performance Status will also be assessed

Analysis of ORR and DoR will be based upon BICR assessment according to RECIST 1.1. See the statistical methods section for further details.

Note: Prior irradiated lesions may be considered measurable and selected as target lesions providing they fulfil the other criteria for measurability.

ADA Anti-drug antibody; AE Adverse event; APF12 Proportion of patients alive and progression free at 12 months from randomisation; APF18 Proportion of patients alive and progression free at 18 months from randomisation; BICR Blinded Independent Central Review; DoR Duration of response; EORTC QLQ-C30 European Organisation for Research and Treatment of Cancer 30-item core quality of life questionnaire; LC13 Lung Cancer Module; ORR Objective response rate; OS24 Proportion of patients alive at 24 months from randomisation; PFS2 Time from randomisation to second progression; PK Pharmacokinetic(s); QoL Quality of Life; RECIST Response Evaluation Criteria In Solid Tumours; TTDM Time to death or distant metastasis.

Exploratory Objective:	Outcome Measure:
To explore irRC criteria as an assessment methodology for clinical benefit of MEDI4736 compared with placebo by BICR	PFS and ORR using BICR assessments according to irRC
To investigate the relationship between MEDI4736 PK exposure and clinical outcomes, efficacy, AEs and/or safety parameters, if deemed appropriate	A graphical and/or a data modelling approach will be used to analyse MEDI4736 PK exposure and the relationship with clinical outcomes, efficacy, AEs and/or safety parameters, as deemed appropriate
To describe and evaluate resource use associated with MEDI4736 treatment and underlying disease	Health resource utilisation measures including hospitalization, outpatient visits, or emergency department visits
To explore the impact of treatment and disease state on health state utility using the EQ-5D-5L	The EQ-5D-5L health state utility index will be used to derive health state utility based on patient reported data
To investigate the relationship between a patient's PD-L1 expression and spatial distribution within the tumour microenvironment and efficacy outcomes with MEDI4736	Tumoural expression of PD-L1 and spatial distribution within the tumour microenvironment relative to efficacy outcomes (OS, PFS and ORR)
To collect blood and tissue samples for analysis of peripheral and tumoural biomarkers	Biomarker analysis of blood and tissue to assess exploratory markers which may include but is not limited to: immune cell gene expression profiles within the peripheral and tumoural compartments, the presence of IFN- $\gamma$ tumour necrosis factor- $\alpha$ , IL-2, IL-6, IL-10, IL-8, and IL-12 as well as antibodies against tumour, self, or viral antigens, expression of PD-L1 and the number and phenotype of immune cells such as T-cells
To explore the relationship(s) between a patient's biomarker status and MEDI4736 PK exposure and clinical outcomes before and after treatment	Biomarker status before and after treatment and MEDI4736 PK exposure and relationship with clinical outcomes, efficacy, AEs and/or safety parameters, as deemed appropriate
To explore potential biomarkers in residual biological samples (eg, tumour, plasma and/or serum), which may influence the progression of cancer (and associated clinical characteristics) and/or prospectively identify patients likely to respond to MEDI4736 treatment	Correlation of biomarkers with response to MEDI4736 treatment and/or the progression of cancer
To collect and store DNA according to each country's local and ethical procedures for future exploratory research into genes/genetic variation that may influence response (ie, distribution, safety, tolerability and efficacy) to study drugs and/or susceptibility to disease (optional)	Correlation of polymorphisms with variation in PK, PDx, safety or response parameters observed in patients treated with MEDI4736 and/or susceptibility to disease

AE Adverse event; BICR Blinded Independent Central Review; EQ-5D-5L EuroQoL 5-dimension, 5-level health state utility index; IFN Interferon; IL Interleukin; irRC Immune-related response criteria; ORR Objective response rate; OS Overall survival; PD-L1 Programmed death ligand 1; PDx Pharmacodynamic(s); PFS Progression free survival; PK Pharmacokinetic(s); T-cell T lymphocyte.

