### **12.2.5 Duration of response**

In order to analyse the DoR between arms the Expected Duration of Response (EDoR) will be derived for each treatment arm (Ellis et al 2008) for the BICR tumour data. The EDoR is the product of the proportion of patients responding to treatment and the mean DoR in responding patients and provides an estimate based on all randomised patients. Treatments will be compared by calculating the ratio of EDoRs, using an appropriate probability distribution (to be specified in the SAP) for DoR in responding patients. Additionally, descriptive data will be provided for the DoR in responding patients, including the associated Kaplan-Meier curves (without any formal comparison of treatment arms or p-value attached).

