### **12.2.6 Proportion of patients alive and progression free at 12 months (APF12)**

The proportion of patients alive and progression free at 12 months will be summarised (using the Kaplan-Meier curve) and presented by treatment arm. Each will be compared between treatments by using the Kaplan-Meier estimator of PFS at 12 months for each treatment to obtain the HR. The HR and CI will be presented.

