### **12.2.7 Proportion of patients alive and progression free at 18 months (APF18)**

The proportion of patients alive and progression free at 18 months will be summarised (using the Kaplan-Meier curve) and presented by treatment arm. Each will be compared between treatments by using the Kaplan-Meier estimator of PFS at 18 months for each treatment to obtain the HR. The HR and CI will be presented.

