Objective Response Rate	Fisher’s exact test using BICR data (RECIST 1.1) Sensitivity analysis using the Fisher’s exact test using site investigator tumour data (RECIST 1.1) Sensitivity analysis using the Fisher’s exact test using BICR tumour data (RECIST 1.1, modified for confirmation of progression) Exploratory analysis using the Fisher’s exact test using BICR tumour data (irRECIST)
Duration of Response	Analysis following the method described by Ellis et al 2008 using BICR tumour data (RECIST 1.1)
Proportion of patients alive and progression free at 12 and 18 months	Kaplan Meier estimates of progression free survival at 12 and 18 months
Time from randomisation to second progression	Stratified log-rank test
Time to death or distant metastasis	Stratified log-rank test using site BICR tumour data (RECIST 1.1)

Table 8 Formal statistical analyses to be conducted and pre-planned sensitivity analyses

Endpoints Analysed	Notes
Symptom improvement rate (EORTC QLQ-C30 and LC13 endpoints)	Logistic regression
HR QoL/Function improvement rate (EORTC QLQ-C30 endpoints)	Logistic regression
Time to HR QoL/Function deterioration (EORTC QLQ-C30 endpoints)	Stratified log-rank test
Time to symptom deterioration (EORTC QLQ-C30 and LC13 endpoints)	Stratified log-rank test
Change from baseline (EORTC QLQ C30 and LC13; EQ-5D-5L health state utility values and Visual Analogue Scale)	Mixed model repeated measures analysis

BICR Blinded Independent Central Review; EORTC QLQ-C30 European Organisation for Research and Treatment of Cancer 30-item core quality of life questionnaire; EQ-5D-5L EuroQoL 5 dimension, 5 level health state utility index; irRC Immune-related response criteria; LC13 Lung Cancer Module; HR QoL Quality of Life; RECIST Response Evaluation Criteria In Solid Tumours.

All outputs will be summarised by treatment arm as randomised for all ITT patients.

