4.2.2.3 Duration of response

Descriptive data will be provided for the DoR in responding patients (ie median duration of response and 95% CIs) by treatment arm, including the associated Kaplan-Meier curves (without any formal comparison of treatment arms or p-value attached).

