4.2.2.4 Proportion of patients alive and progression free at 12 months (APF12)

The proportion of patients alive and progression free at 12 months (i.e. at study day 366) will be summarised (using the Kaplan-Meier curve) and presented by treatment arm. For each treatment arm, the APF12 based on Kaplan-Meier method will be presented, along with its 95% confidence interval. The computation of the confidence interval will be based on a log(-log(.)) transformation.

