4.2.2.5 Proportion of patients alive and progression free at 18 months (APF18)

The proportion of patients alive and progression free at 18 months (i.e. at study day 549) will be summarised (using the Kaplan-Meier curve) and presented by treatment arm. For each treatment arm, the APF18 based on Kaplan-Meier method will be presented, along with its 95% confidence interval. The computation of the confidence interval will be based on a log(-log(.)) transformation.

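### The protocol plans a treatment-effect estimate for APF12, APF18 and DoR; the SAP methods give by-arm figures only, and SAP Table 8 contradicts them on DoR

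*Protocol*

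**What the plan says.** **Objective.** The protocol (Objectives and section 2.2) and SAP section 1.1.2 give the same comparative wording: "To further assess the efficacy of MEDI4736 compared with placebo in terms of: OS24, ORR, DoR, APF12, APF18, PFS2, and TTDM".

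**Protocol methods.** Section 12.2.6, for APF12: "Each will be compared between treatments by using the Kaplan-Meier estimator of PFS at 12 months for each treatment to obtain the HR". Section 12.2.7, for APF18: "Each will be compared between treatments by using the Kaplan-Meier estimator of PFS at 18 months for each treatment to obtain the HR". Both add a CI, and Table 15 repeats the HR. For DoR, section 12.2.5 says: "Treatments will be compared by calculating the ratio of EDoRs". It adds responder-only curves as description.

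**SAP methods.** Section 4.2.2.4: "For each treatment arm, the APF12 based on Kaplan-Meier method will be presented, along with its 95% confidence interval". Section 4.2.2.5: "For each treatment arm, the APF18 based on Kaplan-Meier method will be presented, along with its 95% confidence interval". Neither adds a difference, a ratio or a test. Section 4.2.2.3 gives the median DoR with 95% CI and the Kaplan-Meier curve by arm, in responders, "without any formal comparison of treatment arms or p-value attached".

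**SAP tables.** Table 8, the list of formal analyses, agrees with the text for APF12 and APF18 but keeps the expected-duration method in its DoR row ("et al 2008 using BICR tumour data (RECIST 1.1"). Table 9 declares both departures from the protocol. The DoR analysis is removed as not required, and the APF12 and APF18 presentation is changed to fit table standards.

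**The concern.** The protocol promises an estimate of the treatment effect on each of these endpoints. The SAP keeps the objective but drops the estimate for two of them and says two different things about the third. The protocol supplied (September 2019) is later than the SAP (March 2017) and still contains all three comparisons, so the two documents remain unreconciled.

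The reasons given in Table 9 are not statistical and do not explain how an unchanged comparative objective is met. A reader of the results would have two separate intervals for each landmark and would have to judge the contrast from them. For DoR, the by-arm figures describe responders. Responders are selected after randomisation, so those figures do not compare the randomised arms; the protocol's EDoR was designed to cover all randomised patients. A programmer also cannot follow both Table 8 and section 4.2.2.3.

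**Working it through.** **1. Passages side by side**

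| Endpoint | Protocol | SAP methods text | SAP Table 8 | SAP Table 9 |
|---|---|---|---|---|
| APF12, APF18 | HR with CI (12.2.6, 12.2.7, Table 15) | Estimate and CI per arm (4.2.2.4, 4.2.2.5) | Kaplan-Meier estimates | Change declared |
| DoR | EDoR ratio (12.2.5, Table 15) | Median and curve per arm, responders (4.2.2.3) | Expected-duration method kept | Removal declared |

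The other four endpoints in the objective keep a comparison in the SAP: OS24 (4.2.2.1), ORR (4.2.2.2), PFS2 (4.2.2.6) and TTDM (4.2.2.7). For APF12 and APF18 the SAP is consistent with itself and differs from the protocol. For DoR it also contradicts itself.

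**2. What the missing landmark contrast would look like**

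The plan has no figure of its own to reproduce here. Inputs from SAP section 1.3: exponential PFS with medians of 10 months (placebo) and 15 months (10 + 5); 702 patients randomised 2:1, so 468 and 234. Assumption: complete follow-up to each landmark. Censoring would widen every interval below.

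S(t) = 0.5^(t/median).
- Month 12: placebo 0.5^1.2 = 0.435; MEDI4736 0.5^0.8 = 0.574; difference 13.9 points.
- Month 18: placebo 0.5^1.8 = 0.287; MEDI4736 0.5^1.2 = 0.435; difference 14.8 points.

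The contrast in SAP section 4.2.2.1 is ln[ln S1 / ln S2]. With complete follow-up its variance per arm is (1 − S)/(n·S·(ln S)²).
- Month 12: ln(0.8/1.2) = −0.405; variance 0.00515 + 0.00801 = 0.01316; SE 0.115. HR 0.67, 95% CI exp(−0.405 ± 1.96 × 0.115) = 0.53 to 0.84.
- Month 18: ln(1.2/1.8) = −0.405; variance 0.00401 + 0.00681 = 0.01082; SE 0.104. HR 0.67, 95% CI 0.54 to 0.82.

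Difference in proportions with binomial SEs: month 12, SE 0.0397, 95% CI 6.1 to 21.7 points; month 18, SE 0.0374, 95% CI 7.5 to 22.1 points.

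**3. Reading two intervals by eye**

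On the same inputs and the log(-log) scale, the contrast CI excludes no effect with probability Φ(0.405/SE − 1.96): 94% at month 12 and 97% at month 18. The two arm intervals fail to overlap with probability Φ([0.405 − 1.96(SE1 + SE2)]/SE). With SEs 0.072 and 0.090 at month 12 this is 78%; with 0.063 and 0.083 at month 18 it is about 87%. This shows that overlap is a poor substitute for a contrast. It is not a property of any rule in the plan.

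**4. What restoring EDoR would need**

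Protocol section 12.2.5 leaves the response-duration distribution to the SAP, and the SAP names none. The denominators also differ: section 12.2.5 bases EDoR on all randomised patients, while SAP section 3.2.2.3 ties the DoR denominator to that of ORR, which section 3.2.2.2 limits to patients with measurable disease at baseline. Putting the ratio back without settling both would create a new inconsistency.

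**The case against.** The strongest reply is that little is lost. APF12 and APF18 are defined as points on the PFS Kaplan-Meier curve, and that curve is compared between arms as a co-primary endpoint, with a stratified log-rank test, HR, CI and plots; piecewise HRs follow if hazards are not proportional. Under proportional hazards the dropped landmark HR targets the same quantity less efficiently. The changes are declared in Table 9. The endpoints lie outside the multiple testing procedure, which covers only PFS, OS, OS24 and ORR. The safety objective is also worded as a comparison with placebo and is analysed descriptively. Because the arm CIs use log(-log), a reader could rebuild an unstratified contrast from them.

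Most of this stands, and it limits the size of the point. It does not remove it. The protocol plans safety descriptively but specifies these efficacy contrasts. A contrast that can be rebuilt is not a planned one. The Table 8 contradiction is untouched by any of these arguments.

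A reader might infer more than the documents support:
- *That the comparison is never made.* Table 8 and the protocol still plan it for DoR, and PFS is formally compared.
- *That the overlap probabilities measure a loss of power.* No document proposes judging by overlap.
- *That responder-only DoR will point the wrong way.* This needs invented inputs. Suppose responders rise from 20% to 30% and the added responses last 6 months against 12. Mean DoR is then (0.2 × 12 + 0.1 × 6)/0.3 = 10 against 12 months, while expected time in response is 3.0 against 2.4 months. But the SAP reports medians, and with these two fixed durations they are 12 and 12.
- *That EDoR must be restored.* Its open distribution and denominator make that a choice with costs. The response rate itself is formally compared in any case.

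**Conclusion.** The point holds as a mismatch between protocol and SAP on APF12 and APF18, and as a mismatch plus an internal SAP contradiction on DoR. No landmark treatment-effect estimate is planned, although the objective and the protocol call for one. DoR is left with responder-only summaries that should not be read as a randomised comparison.

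It is worth correcting but does not threaten the trial's conclusions. No alpha, event count, sample size or success criterion depends on it. The 13.9- and 14.8-point differences and their intervals rest on exponential PFS at the design medians, full enrolment and complete follow-up. They show what a reader would gain, and are not a forecast or a measured defect.

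**What to change.** 1. **SAP 4.2.2.4 and 4.2.2.5.** Add the between-arm contrast at study days 366 and 549 with a 95% CI: the log(-log) contrast of SAP section 4.2.2.1, the difference in Kaplan-Meier proportions, or both. Label it supportive and outside the multiple testing procedure. When reusing the section 4.2.2.1 text, leave out its restriction to a sub-study B, which this trial does not have. Update Table 8 and Table 9 to match. The cost is a few table lines.

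2. **DoR: choose one.**
   - Keep the EDoR ratio with its CI, state the response-duration distribution, and state whether the denominator is all randomised patients or those with measurable disease at baseline. Restore it in SAP section 4.2.2.3 and withdraw the removal in Table 9. The cost is a modelling assumption and some programming.
   - Delete the DoR row from SAP Table 8, and say in the objective, Protocol section 12.2.5 and the matching Table 15 row that DoR is descriptive in responders and not a randomised comparison. The cost is wording only, but it needs a protocol change.

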## Study design

This is a Phase III, randomised, double-blind, placebo-controlled, multi-centre study assessing the efficacy and safety of MEDI4736 (also referred to as durvalumab) compared with placebo, as sequential therapy in male and female patients with locally advanced, unresectable NSCLC (Stage III), who have not progressed following definitive, platinum-based, concurrent chemoradiation therapy.

Approximately 1000 patients will be enrolled and 702 patients randomised (patients will be in CR, PR or have SD following definitive, platinum-based, concurrent chemoradiation therapy) at 260 to 330 sites worldwide, in a 2:1 ratio (MEDI4736 to placebo) to 1 of 2 arms:

- MEDI4736 (10 mg/kg every 2 weeks [Q2W] intravenous [iv] for up to 12 months)
- Placebo (matching placebo for infusion Q2W iv for up to 12 months).

Randomisation will be stratified by: age at randomisation (<65 versus  $\geq 65$  years of age), sex (male versus female), and smoking history (smoker versus non-smoker). Patients must complete their last dose of radiation therapy within 1 to 42 days prior to randomisation in the study (the last dose of radiation therapy is defined as the day of the last radiation treatment session). For patients who are recovering from toxicities associated with prior treatment, randomisation may be delayed by up to 42 days from the end of the chemoradiation therapy. For those patients randomised to the placebo arm no cross-in to the MEDI4736 arm is permitted and similarly those patients randomised to the MEDI4736 arm no cross-in to the placebo arm is permitted.

The primary objective of this study is to assess the efficacy of MEDI4736 treatment compared with placebo in terms of overall survival (OS) and progression free survival (PFS) per RECIST 1.1 as assessed by Blinded Independent Central Review (BICR).

Tumour assessments will be performed using computed tomography/magnetic resonance imaging. The baseline assessment is part of the screening procedures and should be performed within 0 to 42 days after the end of chemoradiation therapy and before the start of study drug. Efficacy for all patients will be assessed by objective tumour assessments every 8 weeks (relative to the date of randomisation) for the first 12 months, then every 12 weeks thereafter, until confirmed objective disease progression as defined by Response Evaluation Criteria in Solid Tumours (RECIST) 1.1 (irrespective of the reason for stopping study drug and/or subsequent therapy). If an unscheduled assessment is performed, and the patient has not progressed, every attempt should be made to perform the subsequent assessments at their scheduled visits. A BICR will be conducted.

Following completion or discontinuation of study drug, patients will enter a follow-up period.

Once a patient has had objective progression recorded and has discontinued study drug, the patient will be followed up for survival status every 2 months until death, withdrawal of consent or the end of the study.

There will be 4 DCO time points in the study. The first analysis DCO will occur when it is expected that 367 PFS events have occurred (52% maturity, approximately 30 months after the first patient is randomised). The second analysis DCO will occur at the time of the primary PFS analysis when it is expected that 458 PFS events have occurred (65% maturity, approximately 36 months after the first patient is randomised), and the first OS interim analysis will be conducted at the same time (with approximately 285 events, 41% maturity). The third analysis DCO will occur at the time of the second OS interim analysis when it is expected that 393 OS events have occurred (56% maturity, approximately 47 months after the first patient is randomised). The fourth analysis DCO will occur at the time of the primary OS analysis when it is expected that 491 OS events have occurred (70% maturity, at approximately 62 months). If the study achieves statistical significance for the co-primary endpoints of PFS and/or OS at one of the planned interim analyses, then that will be considered the final analysis for that endpoint. Further analyses for that particular endpoint may occur based on the needs for long term follow-up with more mature data. See the Statistical methods section (Section 12.2) for further details.

At the time of Amendment 07 finalisation, the study endpoints had been met and the planned analysis portion of the study had been concluded. Details on long-term follow up, including data collection for patients in follow-up or in re-treatment, are provided in the Long-term follow up section (Section 9.5).

